6.0 Study Intervention/Investigational Agent

1.1 Description: *Describe the study intervention and/or investigational agent (e.g., drug, device) that is being evaluated.*

Response: HYDRAL Oral rinse and Biotene rinse contain one or more of the following: Sorbitol, Sodium citrate, Propanediol, Polyvinylpyrrolidone, Betaine, PEG-40 Hydrogenated Castor Oil, Xylitol, Taurine, Citric acid, Sodium hydroxide, Methyl paraben, Flavor, Mild Mint flavor, Sodium hyaluronate, Cetylpyridinium chloride, Sucralose, Stevia Redaudiana Extract, Glycerin, Propylene Glycol, Poloxamer 407, Sodium Benzoate, Hydroxyethyl Cellulose, Propylparaben, Sodium Phosphate, Disodium Phosphate

6.1 *Drug/Device Handling: If the research involves drugs or device, describe your plans to store, handle, and administer those drugs or devices so that they will be used only on subjects and be used only by authorized investigators.*

- *If the control of the drugs or devices used in this protocol will be accomplished by following an established, approved organizational SOP (e.g., Research Pharmacy SOP for the Control of Investigational Drugs, etc.), please reference that SOP in this section.*

Response: An inventory of the study products and dispensing logs will be maintained by the Clinical Coordinator. Unused materials will be disposed.

6.2 *If the drug is investigational (has an IND) or the device has an IDE or a claim of abbreviated IDE (non-significant risk device), include the following information:*

- *Identify the holder of the IND/IDE/Abbreviated IDE.*
- *Explain procedures followed to comply with sponsor requirements for FDA regulated research for the following:*

FDA Regulation	Applicable to:		
	IND Studies	IDE studies	Abbreviated IDE studies
21 CFR 11	X	X	
21 CFR 54	X	X	
21 CFR 210	X		
21 CFR 211	X		
21 CFR 312	X		
21 CFR 812		X	X
21 CFR 820		X	

Response: The device is not investigational and is in commercial use. The device holds a 510(K) by the FDA (attached in devices section of the IRB submission portal).

7.0 Local Number of Subjects

7.1 *Indicate the total number of subjects that will be enrolled or records that will be reviewed locally.*

Response: 39

7.2 *If applicable, indicate how many subjects you expect to screen to reach your target sample (i.e. your screen failure rate).*

Response: We anticipate screening 125 subjects to reach our target sample of 39.

7.3 *Justify the feasibility of recruiting the proposed number of eligible subjects within the anticipated recruitment period. For example, how many potential subjects do you have access to? What percentage of those potential subjects do you need to recruit?*

8.0 Inclusion and Exclusion Criteria

Response: The number of subjects needed for this study is based on the feasibility of the study. *Inclusion and Exclusion Criteria**

8.1 *Describe the criteria that define who will be **included** in your final study sample.*

NOTE: This may be done in bullet point fashion.

Response: Individuals may be included in the study provided they meet all of the following inclusion criteria:

- Must have read, understood and signed an informed consent prior to being entered into the study,
- Must be 18 to 80 years of age, male or female,
- Have at least 20 natural or restored teeth,
- Have a complaint of xerostomia,

- Have an unstimulated salivary flow rate <0.20 ml/minute which represents a significant reduction of normal salivary function, 6) Must have subjective xerostomia symptom: minimum level of 4 on a 10 centimeters Visual Analog Scale (VAS). The question, using a VAS scale, would be "How would you score your dryness on the basis of a scale of 1 to 10?" and on the left would be zero, and on the right would be severe (10). They would have to score a 4 or higher to be in the study. We would ask this same question both before and after the two week usage period,
- Agree not to have a dental prophylaxis or any other elective, non-emergency dental procedures (other than those provided during the study) any time during the study,
- Agree to abstain from the use of any products for xerostomia other than those provided in the study
- Agree to comply with the conditions and schedule of the study.

8.2 Describe the criteria that define who will be **excluded** from your final study sample.

NOTE: This may be done in bullet point fashion.

Response: Individuals are not eligible for participation in this study if any of the following are noted:

- Physical limitations or restrictions that might preclude normal tooth brushing.
- Evidence of gross oral pathology, including widespread caries or chronic neglect, extensive restoration, pre-existing gross plaque or soft or hard tissue tumor of the oral cavity.
- Presence of severe gingivitis with 30 or more sites showing bleeding on probing.
- Evidence of major oral hard or soft tissue lesions or trauma at the baseline visit as determined by the Investigator/Examiner.
- Chronic disease with concomitant oral manifestations other than xerostomia
- Conditions requiring antibiotic treatment prior to dental prophylaxis and invasive procedures, such as heart murmur, history of rheumatic fever, valvular disease or certain prosthetic implants.
- History of hepatic or renal disease, uncontrolled diabetes, or other serious conditions or transmittable diseases.
- Taking concomitant medications which may interfere with oral tissues such as anticoagulants, NSAID's, and those shown to enlarge gingival tissues.

- A positive pregnancy test at visit one would also cause your removal from the study.
- Subjects who are currently undergoing, or require, extensive dental work, orthodontic treatment or periodontal surgery or orthodontic treatment in the preceding 3 months
- Currently using bleaching trays
- History of radiotherapy, head and neck cancer or Sjogren's syndrome.
- History of significant adverse effects following use of oral hygiene products such as toothpastes and mouthrinses.
- Subjects who are nursing, pregnant or plan to become pregnant for the duration of the study.
- Eating disorders
- Recent history of substance abuse
- Participation in other clinical studies within 14 days of screening
- Smoking >10 cigarettes/day
- Chewing tobacco
- Daily use of symptom alleviating products against xerostomia within 7 days of screening.

8.3 *Indicate specifically whether you will include any of the following special populations in your study using the checkboxes below.*

NOTE: Members of special populations may not be targeted for enrollment in your study unless you indicate this in your inclusion criteria.

Response:

- Adults unable to consent
- Individuals who are not yet adults (infants, children, teenagers)
- Pregnant women
- Prisoners

8.4 *Indicate whether you will include non-English speaking individuals in your study. **Provide justification if you will exclude non-English speaking individuals.***

*In order to meet one of the primary ethical principles of equitable selection of subjects, non-English speaking individuals may **not** be routinely excluded from research as a matter of convenience.*

In cases where the research is of therapeutic intent or is designed to investigate areas that would necessarily require certain populations who

may not speak English, the researcher is required to make efforts to recruit and include non-English speaking individuals. However, there are studies in which it would be reasonable to limit subjects to those who speak English. Some examples include pilot studies, small unfunded studies with validated instruments not available in other languages, studies with numerous questionnaires, and some non-therapeutic studies which offer no direct benefit.

Response: Non-English speaking individuals will be included only if adequate translation support can be obtained. We will include a copy of written informed consent to the IRB in a translated format prior to enrolling of a subject who requires translation.

9.0 Vulnerable Populations*

If the research involves special populations that are considered vulnerable, describe the safeguards included to protect their rights and welfare.

NOTE: You should refer to the appropriate checklists, referenced below, to ensure you have provided adequate detail regarding safeguards and protections. You do not, however, need to provide these checklists to the IRB.

9.1 For research that involves **pregnant women**, safeguards include:
NOTE CHECKLIST: Pregnant Women (HRP-412)

Response:

N/A: This research does not involve pregnant women.

9.2 For research that involves **neonates of uncertain viability or non-viable neonates**, safeguards include:
NOTE CHECKLISTS: Non-Viable Neonates (HRP-413), or Neonates of Uncertain Viability (HRP-414)

Response:

N/A: This research does not involve non-viable neonates or neonates of uncertain viability.

9.3 For research that involves **prisoners**, safeguards include:
NOTE CHECKLIST: Prisoners (HRP-415)

Response:

N/A: This research does not involve prisoners.

9.4 For research that involves **persons who have not attained the legal age for consent to treatments or procedures involved in the research (“children”)**, safeguards include:
NOTE CHECKLIST: Children (HRP-416)

Response:

N/A: This research does not involve persons who have not attained the legal age for consent to treatments or procedures (“children”).

9.5 For research that involves **cognitively impaired adults**, safeguards include:
NOTE CHECKLIST: *Cognitively Impaired Adults (HRP-417)*

Response:

N/A: This research does not involve cognitively impaired adults.

9.6 Consider if other specifically targeted populations such as students, employees of a specific firm, or educationally or economically disadvantaged persons are vulnerable. **Provide information regarding their safeguards and protections, including safeguards to eliminate coercion or undue influence.**

Response: N/A

10.0 Eligibility Screening*

10.1 Describe **screening procedures** for determining subjects’ eligibility. Screening refers to determining if prospective participants meet inclusion and exclusion criteria.

 Include all relevant screening documents with your submission (e.g. screening protocol, script, questionnaire).

Response: Seven days before screening visit potential subjects shall be advised to stop using their usual dry mouth remedy. Since some mouthrinses and other oral hygiene products have a residual effect on oral tissues, we are asking the potential subjects to cease using these products for one week prior to their visit so that we can evaluate the status of their oral tissues. Male and female subjects will read and sign the informed consent prior to enrollment. Subjects will be asked about demographics, medical history, general health status and current medication usage, and the information will be recorded.

The subjects will be asked if they currently experience any problems such as burning, stinging, irritation, etc., and if so, the nature of the effect, severity and onset time (if known) will be recorded.

VAS scoring of lubrication or moisture of your mouth will be scored and unstimulated saliva flow will be measured (Inclusion Criteria). A qualified dental examiner will perform an oral soft and hard tissue examination (OST) to verify that the subjects meet the inclusion and exclusion criteria.

Following the OST exam, qualifying subject’s unstimulated saliva will be collected over a 5 minutes time period and the volume measured to determine if they meet the study criteria for xerostomia. VAS question related to symptoms of xerostomia will be completed (≥ 4 cm is required for inclusion). Subjects will

also be asked to refrain from eating or drinking for 1 hour prior to being examined.

Upon completion of the screening visit, the Principal Investigator or his designee will review subject screening reports and determine whether or not the subject qualifies for study enrollment. If the subject qualifies, an appointment date will be set for Visit 1 which could be immediately follow the screening exam.

N/A: There is no screening as part of this protocol.

11.0 Recruitment Methods

N/A: This is a records review only, and subjects will not be recruited. NOTE: If you select this option, please make sure that all records review procedures and inclusion/exclusion screening are adequately described in other sections.

11.1 Describe when, where, and how potential subjects will be recruited.

NOTE: Recruitment refers to how you are identifying potential participants and introducing them to the study. Include specific methods you will use (e.g. searching charts for specific ICD code numbers, Research Participant Groups, posted advertisements, etc.).

Response:

The study will be advertised in UB dental school clinics and on UB campuses. The subjects will be recruited over a period of approximately 3 months following IRB approval using flyers (uploaded on click IRB) which will be posted in the aforementioned places. The advertisement will also be posted on the UB Dental School website, and UB's Participate in Research Portal. Also, the study team will utilize UB's Clinical and Translational Science Institute for recruitment assistance and consultation.

Patients who are interested in participating will be questioned according to a standard telephone script designed to include inclusion/exclusion criteria (uploaded on click IRB). If eligible to be included, subjects will be invited for a screening exam at the Center for Dental Studies, UB School of Dental Medicine

11.2 Describe how you will protect the privacy interests of prospective subjects during the recruitment process.

NOTE: Privacy refers to an individual's right to control access to him or herself.

Response: Potential participants are contacting the research team if interested in participating and are therefore controlling their own privacy interests during recruitment. The center for clinical dental research is a private space that allows data collection while maintaining privacy of the patient. In addition, the data collection, storage, communication and analysis will be carried out in compliance with privacy regulations of University at Buffalo and the School of Dental Medicine.

11.3 Identify any materials that will be used to recruit subjects.

NOTE: Examples include scripts for telephone calls, in person announcements / presentations, email invitations.

 *For advertisements, include the final copy of printed advertisements with your submission. When advertisements are taped for broadcast, attach the final audio/video tape. NOTE: You may submit the wording of the advertisement prior to taping to ensure there will be no IRB-required revisions, provided the IRB also reviews and approves the final version.*

Response: Flyers will be used for recruitment. These documents have been attached in the IRB submission online. Patients who are interested in participating will be questioned according to a standard telephone script designed to include inclusion/exclusion criteria (uploaded on click IRB). If eligible to be included, subjects will be invited for a screening exam at the Center for Dental Studies, UB School of Dental Medicine.

12.0 Procedures Involved*

12.1 Provide a description of **all research procedures or activities** being performed and when they are performed once a subject is screened and determined to be eligible. Provide as much detail as possible.

NOTE: This should serve as a blueprint for your study and include enough detail so that another investigator could pick up your protocol and replicate the research. For studies that have multiple or complex visits or procedures, consider the addition of a schedule of events table in in your response.

Response: **If a potential patient is a mouthrinse user, we will be sending them a Consent Form for the study which they will be asked to read, sign and date and return to us. Also, If they have any concerns or questions, we will discuss with them. Once we receive the signed consent form, we will give patients a screening visit appointment, and remind them to cease use of any mouthrinses for 7 days prior to the appointment.** At the screening visit, every potential subject will be consented again and interviewed. Subjects who sign the Informed Consent Form and meet eligibility criteria will then have an Oral Screening Examination by the Primary Examiner. After review of the results of the Informed Consent, Screening Interview and Screening Oral Examination, the Principal Investigator or designee will determine whether or not a subject should be enrolled in the study.

Screening

Seven days before screening visit potential subjects shall stop using their usual dry mouth mouthrinse as outlined above.. Male and female subjects will again read and sign the informed consent with a staff member of the study as a witness.. Since some mouthrinses have a residual effect on oral tissues, we are asking the potential subjects to cease using these products for one week prior to their visit so that we can evaluate the status of their oral tissues . Interested patients will be contacted at least 7 days prior to the screening visit to read, sign and date the Consent Form and then start the one week withdrawal of current mouthrinse

before coming to the screening visit. The study team will then call the patient after the Consent Form is mailed to answer any questions or concerns that they may have. The patient can mail the Consent Form back in a stamped self-addressed envelope. The withdrawal of mouthrinse can begin once the study team receives the Consent Form and notifies the patient of its receipt. Subjects will be asked about demographics, medical history, general health status and current medication usage, and the information will be recorded.

The subjects will be asked if they currently experience any problems such as burning, stinging, irritation, etc., and if so, the nature of the effect, severity and onset time (if known) will be recorded.

VAS scoring of lubrication or moisture of your mouth will be scored and unstimulated saliva flow will be measured (Inclusion Criteria). A qualified dental examiner will perform an oral soft and hard tissue examination (OST) to verify that the subjects meet the inclusion and exclusion criteria.

Following the OST exam, qualifying subject's unstimulated saliva will be collected over a 5 minutes time period and the volume measured to determine if they meet the study criteria for xerostomia. VAS question related to symptoms of xerostomia will be completed (≥ 4 cm is required for inclusion). Subjects will also be asked to refrain from eating or drinking for 1 hour prior to being examined.

If the patient meets the study criteria and has time to participate in visit 1, they may enter the study following the screening visit. If acceptable for the study, this screening visit will serve as their Visit I baseline.

Visit I

This visit will last approximately 1 hour. The following will happen at this visit: Subjects will be asked to refrain from eating or drinking for 1 hour prior to being examined. If Screening visit and Visit 1 don't happen at the same day, the study staff will update Inclusion/Exclusion Criteria, medical history and concurrent medications.

Subjects will complete VAS question (Appendix A), Xerostomia questionnaire (Appendix B) and Oral Health Impact Profile -14 (OHIP-14) (Appendix C) for the baseline information.

A qualified dental examiner will perform an oral soft and hard tissue examination (OST), unstimulated saliva flow measurement and the objective assessment of oral health condition using the standardized instrument, Revised Oral Assessment Guide (ROAG) (Appendix D). Some intraoral photographs will be taken.

They will then be given their assigned product to use four times daily for two weeks. Subjects will maintain a daily diary (Appendix E) of their product usage and any oral effects they experience and will answer all diary questions. Compliance will be assessed by subject diary and measurement of when unused portion is returned to the clinic.

The subjects will be instructed not to use any other xerostomia products for the duration of the study and to follow their normal oral hygiene procedures. All subjects will be provided with a soft toothbrush and regular fluoride toothpaste to use during the study. Subjects will be scheduled to return in approximately 2 weeks, and will be instructed to refrain from eating and drinking for approximately 1 hour prior to their next visit. They will be advised to follow the instructions carefully and return to the study center with their assigned mouthrinse, and diary after 2 weeks for their next examination. Subjects will receive a reminder call prior to Visit 2.

Visit 2

After 2 weeks, subjects will return to the office to return their diary. This visit will last approximately 1.5 hour. The following will happen at this visit: The study staff will update of medical history and concurrent medications. Adverse experiences will be noted and recorded during the study.

The study examiner will perform ROAG(Appendix D) to assess the subject's oral health condition.

Subjects will complete VAS question (Appendix A), Xerostomia questionnaire (Appendix B) and OHIP-14 (Appendix C) for after 2 weeks use of the first product. At Visit 2, they will also complete Product Performance and Attributes Questionnaire for the first product (Appendix F).

A qualified dental examiner will perform OST, unstimulated saliva flow measurement and the objective measurement of xerostomia symptoms (Appendix D). Some intraoral photographs will be taken.

Subjects will then remain in the study center for 60 minutes to evaluate whether their mouth feels moist or lubricated, xerostomia relief by questionnaire at 5, 15, 30, 45 and 60 minutes after the in-office use of their assigned product rinse (Appendix G).

Visit 3

After a 1-week washout, subjects will return to the office to begin the second period of the study, using the same study procedures and be assigned the alternate treatment rinse as in Visit 1.

At the end of Visit 4 (examination for the second product) they will go through a 1 week wash out period and then return for Visit 5 (baseline for the third product) and study will be completed in visit 6.

12.2 Describe what data will be collected.

NOTE: For studies with multiple data collection points or long-term follow up, consider the addition of a schedule or table in your response.

Response: The various data collection points are shown in Table 1 (Study Schedule).

Events	Screening	Visit 1	Visit 2	Visit 3	Visit 4	Visit 5	Visit 6
		First product		Second product		Third product	
Informed Consent, Demographics, Inclusion/Exclusion Criteria, Medical History, Concurrent meds	X						
Demographics Questionnaire	X						
Oral Soft/Hard Tissue Exam & Photos		X	X	X	X	X	X
Update of Inclusion/Exclusion Criteria, Medical History and Conmeds		X	X	X	X	X	X
Unstimulated saliva flow	X (<0.2)	X	X	X	X	X	X
VAS	X (>=4)	X	X	X	X	X	X
Questionnaires (Xerostomia, QoL)		X	X	X	X	X	X
Objective xerostomia endpoint (ROAG)		X	X	X	X	X	X
Product Distribution		X	X	X	X	X	X
Diary Disbursement		X		X		X	
Compliance Check			X		X		X
Product Attribute Questionnaire			X		X		X
Immediate Post-Rinse Evaluation			X		X		X
Adverse Events			X	X	X	X	X

12.3 List any instruments or measurement tools used to collect data (e.g. questionnaire, interview guide, validated instrument, data collection form).

Include copies of these documents with your submission.

Response:

- a. Demographics Questionnaire
- b. Intraoral camera
- c. Medical History
- d. VAS question (Appendix A),
- e. Xerostomia questionnaire (Appendix B)
- f. Oral Health Impact Profile -14 (OHIP-14) (Appendix C)
- g. Revised Oral Assessment Guide (ROAG) (Appendix D)
- h. Daily Diary (Appendix E)
- i. Product Performance and Attributes Questionnaire for the first product (Appendix F)
- j. Immediate Post-Rinse Evaluation (Appendix G)
- k. Oral soft and hard tissue examination form
- l. *Unstimulated saliva flow measurement form*
- m. *Adverse Events form*

12.4 Describe any source records that will be used to collect data about subjects (e.g. school records, electronic medical records).

Response: No source records will be used to collect data about subjects.

12.5 Indicate whether or not **individual** subject results, such as results of investigational diagnostic tests, genetic tests, or incidental findings will be shared with subjects or others (e.g., the subject's primary care physician) and if so, describe how these will be shared.

Response: The data collected in the study will not be shared with the subjects or a third party. The data will be used solely for purposes of this investigation

12.6 Indicate whether or not **study** results will be shared with subjects or others, and if so, describe how these will be shared.

Response: The data collected in the study will not be shared with the subjects or a third party. The data will be used solely for purposes of this investigation. Results post-completion of the study may be published in a de-identified format.

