16.0 Resources and Qualifications

*16.1 Describe the qualifications (e.g., education, training, experience, expertise, or certifications) of the Principal Investigator **and** staff to perform the research. When applicable describe their knowledge of the local study sites, culture, and society. Provide enough information to convince the IRB that you have qualified staff for the proposed research.*

NOTE: If you specify a person by name, a change to that person will require prior approval by the IRB. If you specify a person by role (e.g., coordinator, research assistant, co-investigator, or pharmacist), a change to that person will not usually require prior approval by the IRB, provided that the person meets the qualifications described to fulfill their roles.

Response: The principal investigator (PI) has extensive experience in clinical dental research. The PI has conducted over 60 clinical trials spanning 45 years. In addition, the support staffs in the study have undergone professional training (including dentistry and dental hygiene) to render dental examinations and care and have collaborated with the PI on multiple projects. The clinical coordinator has been associated with the Center for over 20 years.

Describe other resources available to conduct the research.

16.2 Describe the time and effort that the Principal Investigator and research staff will devote to conducting and completing the research.

NOTE: Examples include the percentage of Full Time Equivalents (FTE), hours per week. The question will elicit whether there are appropriate resources to conduct the research.

Response: PI-2%, Study Coordinator 10%, Study Examiner 16%

16.3 Describe the availability of medical or psychological resources that subjects might need as a result of anticipated consequences of the human research, if applicable.

NOTE: One example includes: on-call availability of a counselor or psychologist for a study that screens subjects for depression.

Response: If an adverse event occurs, the subject may be scheduled for a follow-up or under the direction of the Principal Investigator referred to a physician or dentist for treatment. Serious Adverse Events will be followed to the extent of resolution possible. Also, Subjects enrolled in the study may elect to withdraw at any time for any reason.

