21.0 Provisions to Monitor the Data to Ensure the Safety of Subjects*

- N/A: This study is not enrolling subjects, or is limited to records review procedures only. This section does not apply.

NOTE: Minimal risk studies may be required to monitor subject safety if the research procedures include procedures that present unique risks to subjects that require monitoring. Some examples include: exercising to exertion, or instruments that elicit suicidality or substance abuse behavior. In such cases, N/A is not an acceptable response.

21.1 Describe the plan to periodically evaluate the data collected regarding both harms and benefits to determine whether subjects remain safe.

Response: In addition to the efficacy parameters, safety parameters will be collected by members of the research team. This will ensure a study with minimal risk to the participants and early detection of adverse reactions. If an adverse event occurs, the subject may be scheduled for a follow-up or under the direction of the Principal Investigator referred to a physician or dentist for treatment. Serious Adverse Events will be followed to the extent of resolution possible. The Principal Investigator will note the follow-up and resolution of Adverse Events on the Adverse Events Form (uploaded to click IRB). All serious or unsuspected adverse events will be reported to the IRB. Any Serious Adverse Events that occur during the clinical study period will be reported promptly by the Principal Investigator to the IRB within 24 hours of receiving the information.

21.2 Describe what data are reviewed, including safety data, untoward events, and efficacy data.

Response: Study personnel will make note of any health issues they observe or that the subject mentions spontaneously. Recording will include expected or unexpected Adverse Events such as illnesses, injuries, accidents, reactions to a concomitant medication, or worsening of a progressive disease state. An evaluation of the subject's extra- and intra- oral tissues will also be conducted to determine whether any visible adverse response to the test article occurred. In addition subjects will be queried about any other signs or symptoms they have noticed during the course of the study. Adverse events will be evaluated by the

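### Section 12.5 rules out sharing individual results, incidental findings included, with no exception for a suspected oral tumour found at the screening exam

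*Combined protocol and SAP*

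**What the plan says.** The template question at 12.5 covers individual subject results and asks whether such results or "incidental findings will be shared with subjects or others", giving the primary care physician as an example of a recipient. The response is "The data collected in the study will not be shared with the subjects or a third party", followed by a sentence limiting use of the data to this investigation. Nothing is carved out.

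Section 12.6, on study results, repeats the same two sentences and then adds one permitted release: "Results post-completion of the study may be published in a de-identified format".

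The screening examination is described in Sections 10.1 and 12.1. A qualified dental examiner is to "perform an oral soft and hard tissue examination (OST) to verify that the subjects meet the inclusion and exclusion criteria". Among the exclusions in Section 8.2 is a "soft or hard tissue tumor of the oral cavity". Section 10.1 sets out the next step for those who pass: "If the subject qualifies, an appointment date will be set for Visit 1". It gives no step for those who do not.

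**The concern.** The screening exam is performed partly to detect lesions that bar a person from the trial. Someone excluded for a suspected tumour needs to be told, so that they can seek care. Item 12.5 is the one place in the protocol that asks about this, and its answer, followed literally, withholds the finding.

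No passage orders an examiner to stay silent. The fault is narrower: the stated rule, as worded, reaches such findings, and no visible provision lifts it for people who fail screening.

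**Working it through.** There is no plan figure to reproduce. The check sets the passages side by side and asks three questions.

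**1. Does the rule in 12.5 reach the screening exam?**

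- Section 18.2 says that data are collected, with consent, to establish whether the eligibility criteria are met.
- Section 12.3 (item k) lists the oral tissue examination form among the data collection instruments.
- Sections 10.1 and 12.1 both describe the exam at screening, and consent is signed first.
- Against this, Table 1 does not tick the tissue exam under Screening; its ticks start at Visit 1. Two narrative sections place the exam at screening, however, and 12.1 allows an acceptable screening visit to serve as the Visit 1 baseline.

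On balance the exam findings fall within the data collected in the study.

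**2. Does any visible provision override 12.5 for a person excluded at that exam?**

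| Section | Trigger | What it provides | Written for a person excluded at screening? |
|---|---|---|---|
| 16.3 | Adverse event | Possible follow-up or referral | No |
| 21.1 | Adverse event | Possible follow-up or referral | No |
| 22.2 | Withdrawal from the study | Close-out evaluation, if the subject agrees | No |

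The count is 0 of 3. The referral text in 16.3 reads "If an adverse event occurs, the subject may be scheduled for a follow-up or under the direction of the Principal Investigator referred". Section 21.1 is tied to the same trigger: "If an adverse event occurs, the subject may be scheduled for a follow-up". A lesion already present before any product is dispensed is not described anywhere as an adverse event. Section 21.2 has staff record health issues they observe, but does not say that the person is told; it is recording only and is not counted. Someone removed at a separate Visit 1 may come under the 22.2 close-out and is outside this point.

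**3. How many people could be affected?**

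Section 7.2 expects 125 screened for 39 enrolled, so 125 − 39 = 86 would be screened and not enrolled. The documents do not say how many of these would reach the oral exam, or how many would be excluded because of what it shows. On the planned numbers the affected group lies between 0 and 86. The upper end is only a ceiling, since it includes every other reason for non-enrolment.

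**The case against.** The strongest reply is that the sentence is general confidentiality text. Section 20.1 describes collected data as coded forms, and 12.6 uses identical wording for study results, so the authors may have meant study records and not what a dentist says to the person in the chair. Other sections do let individual information move: referral after an adverse event, serious adverse event reports to the IRB, and transfer of data to the biostatistician. The authors plainly did not treat 12.5 as absolute. The exam is done by qualified dental staff in a dental school, who would very probably speak up. A telephone script screens callers on the criteria first, so some known tumours would be caught before any exam. The consent form (HRP-502), the consent procedure (HRP-090) and the examination form are not visible, and any of them could contain a disclosure step.

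Much of this stands as explanation. It makes deliberate withholding unlikely, narrows the group to people with a previously unrecognised lesion, and means one cannot say that no disclosure route exists. It does not change what 12.5 says. The question names incidental findings, and the reply to it is an unqualified refusal. Section 12.6 shows that the authors could add a permitted release where they wanted one. A dentist who told the person would be acting rightly, but against the stated rule. If the consent form does promise disclosure, the practical harm largely goes and a conflict between the two documents remains, which still needs correcting. The count of 0 of 3 describes coverage and does not measure risk.

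**Conclusion.** The concern holds. As written, 12.5 covers a suspected oral tumour found at the screening exam in a person who is then excluded, and none of the 3 visible referral or close-out provisions applies to that person. The conclusion rests on two readings: that data collected in the study include the screening examination, which 12.3 and 18.2 support, and that a pre-existing lesion is not an adverse event.

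The frequency is unknown and probably small, but the consequence for one person left uninformed could be serious. The correction should be made on participant-safety grounds; there is no effect on sample size, endpoint or analysis. Confidence is medium, because the consent form cannot be seen.

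**What to change.** Replace the answer to 12.5 with wording such as:

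> Study data are not shared, except that the examiner tells the person of any clinically relevant examination finding, including one that led to exclusion, and advises or refers them to a dentist or physician.

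Then check that the consent form (HRP-502) says the same. The cost is one sentence and that check. No visit, procedure or data item is added, because the examination is already being done.
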